7.4.4 Electrocardiograms

Descriptive statistics will be provided by treatment for 12-lead ECG interval data (Heart rate, PR interval, QRS duration, QT interval, and RR interval) and changes from baseline for each scheduled visit. The ECG overall interpretation categories (Normal, Abnormal not clinically significant, and Abnormal clinically significant) will be summarized by visit.

All ECG measurements and the overall interpretation will be listed by treatment and subject.

7.4.5 Physical Examinations

Physical examination data will be listed by treatment and subject.

7.4.6 Other Safety Assessments

Other safety assessments not summarized in the sections above will be listed by treatment and subject.

7.5 Efficacy Assessment

The efficacy analysis will be performed based on the MITT Population and will be repeated on the ITT Population.

In efficacy analyses, pairwise contrasts comparing each of the three active groups to the combined placebo group will be tested. Efficacy analyses will be conducted using two sided tests at the alpha=0.05 level of significance, with no adjustment for multiplicity.

7.5.1 Efficacy Endpoints

7.5.1.1 Time (weeks) to First Decrease of BKV Plasma Viral Load by 1 Log

Time (weeks) to first decrease of BKV plasma viral load by >1 log is defined as the number of days from first dose date of study drug to the first decrease of BKV plasma viral load during the study by 1 log from baseline plus 1, then divided by 7.

Subjects who did not have a decrease of BKV plasma viral load by >1 log at any post-baseline visits, discontinued from the study, or died will be considered censored. For the censored subjects, the last assessment date will be used as the date of censoring.

The number and percentage of subjects with a decrease of BKV plasma viral load by 1 log during the study and subjects who are censored will be tabulated. Time to first decrease of BKV plasma viral load by 1 log will be summarized using descriptive statistics.

The median time to first decrease of BKV plasma viral load by 1 log and associated 95% confidence interval (CI) will be estimated for each treatment group using the Kaplan-Meier method. The estimate of the hazard ratio for the treatment comparison between each treatment dose group and the combined placebo group along with the 95% CI will be calculated using a Cox proportional hazard model with treatment (four levels) as a factor. The log-rank p-value for the treatment comparison will be presented as well.

Time (weeks) to first decrease of BKV plasma viral load by >1 log will also be summarized by baseline BKV genotype.

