3 SAMPLE SIZE DETERMINATION

This study will randomize approximately 36 subjects (12 per cohort) to MAU868 and placebo in a 2:1 ratio (24 MAU868 and 12 placebo; 8 MAU868 and 4 placebo per cohort). This study is not powered to an efficacy endpoint. The number of subjects chosen will provide data useful in determining proof of concept.

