7.5.1.2 Time (weeks) to First Decrease of BKV Plasma Viral Load to <LLOQ

The lower limit of quantitation (LLOQ) of BKV plasma viral load is 39 copies/mL BK virus DNA detected <LLOQ will be reported as 'Detected:<39 copies/mL' in data.

Time (weeks) to first decrease of BKV plasma viral load to <LLOQ is defined as the number of days from first dose date of study drug to the first decrease of BKV plasma viral load to <LLOQ during the study plus 1, then divided by 7.

Subjects who did not have a decrease of BKV plasma viral load to <LLOQ at any post-baseline visits, discontinued from the study, or died will be considered censored. For the censored subjects, the last assessment date will be used as the date of censoring.

The number and percentage of subjects with a decrease of BKV plasma viral load to <LLOQ during the study and subjects who are censored will be tabulated. Time to first decrease of BKV plasma viral load to <LLOQ will be summarized using descriptive statistics.

The median time to first decrease of BKV plasma viral load to <LLOQ and associated 95% CI will be estimated for each treatment group using the Kaplan-Meier method. The estimate of the hazard ratio for the treatment comparison between each treatment dose group and the combined placebo group along with the 95% CI will be calculated using a Cox proportional hazard model with treatment (four levels) as a factor. The log-rank p-value for the treatment comparison will be presented as well.

Time (weeks) to first decrease of BKV plasma viral load to <LLOQ will also be summarized by baseline BKV genotype.

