7.5.1.3 Time (weeks) to First Decrease of BKV Plasma Viral Load to <LOD

The limit of detection (LOD) of BKV plasma viral load is 26 copies/mL. BK virus DNA detected <LOD will be reported as 'Not Detected' in data.

Time (weeks) to first decrease of BKV plasma viral load to <LOD is defined as the number of days from first dose date of study drug to the first decrease of BKV plasma viral load to <LOD during the study plus 1, then divided by 7.

Time (weeks) to first decrease of BKV plasma viral load to <LOD will be analyzed in the same manner as Time (weeks) to first decrease of BKV plasma viral load to <LLOQ.

7.5.1.4 Proportion of Subjects with ≥ 1 log Decrease of BKV Plasma Viral Load by Visit

The number and percentage of subjects with ≥ 1 log decrease of BKV plasma viral load by 1 week, 2 weeks, 4 weeks, 8 weeks, 12 weeks, 16 weeks and 36 weeks will be tabulated. The last observation by the specified timepoint will be used to identify ' ≥ 1 log decrease of BKV plasma viral load'.

The proportion of subjects with ≥ 1 log decrease of BKV plasma viral load by the specified visit will be analyzed using a logistic regression model with treatment (four levels) as a factor. For the treatment comparison between each treatment dose group and combined placebo group, the estimated odds ratio, 95% CI, and p-value will be presented.

In addition, the pairwise treatment comparisons in the proportion will be made using Fisher's Exact Test. The treatment difference estimates, the exact 95% CI, and p-values from Fisher's Exact Test will be presented.

The proportion of subjects with ≥ 1 log decrease of BKV plasma viral load by the specified visit will also be summarized by baseline BKV genotype.

7.5.1.5 Proportion of Subjects with Decrease of BKV Plasma Viral Load to <LLOQ by Visit

The number and percentage of subjects with decrease of BKV plasma viral load to <LLOQ by 1 week, 2 weeks, 4 weeks, 8 weeks, 12 weeks, 16 weeks and 36 weeks will be tabulated. The last observation by the specified timepoint will be used to identify 'decrease of BKV plasma viral load to <LLOQ'.

The proportion of subjects with decrease of BKV plasma viral load to <LLOQ by the specified visit will be analyzed using a logistic regression model with treatment (four levels) as a factor. For the treatment comparison between each treatment dose group and combined placebo group, the estimated odds ratio, 95% CI, and p-value will be presented.

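### The censoring sentence for the viral-load time-to-event endpoints does not limit discontinuation or death to subjects without an earlier response, which contradicts the endpoint definition

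*SAP*

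**What the plan says.** SAP 7.5.1.1 measures time from first dose to the "first decrease of BKV plasma viral load during the study by 1 log from baseline plus 1, then divided by 7". The next paragraph says that subjects with no such decrease "at any post-baseline visits, discontinued from the study, or died will be considered censored". The date follows: "For the censored subjects, the last assessment date will be used as the date of censoring". The section then tabulates subjects with a decrease "during the study and subjects who are censored will be tabulated", and goes on to Kaplan-Meier medians, a four-level Cox model and log-rank p-values.

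SAP 7.5.1.2 uses the same construction for <LLOQ: "Subjects who did not have a decrease of BKV plasma viral load to <LLOQ at any post-baseline visits, discontinued from the study, or died" are censored. SAP 7.5.1.3 has no censoring rule of its own; time to <LOD "will be analyzed in the same manner as Time (weeks) to first decrease of BKV plasma viral load to <LLOQ". SAP 8.2.2 applies the Section 7.5.1 methods to the 1-log and <LLOQ endpoints at the second interim.

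Tests are "two sided tests at the alpha=0.05 level of significance, with no adjustment for multiplicity". The planned size is "24 MAU868 and 12 placebo; 8 MAU868 and 4 placebo per cohort", so each contrast in the final analysis compares 8 active subjects with 12 pooled placebo subjects.

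**The concern.** The sentence lists three conditions joined by 'or': no decrease, discontinued from the study, died. Only the first depends on the subject's response. Read as written, leaving the study or dying is enough for censoring, even if the response came months earlier.

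That conflicts with the definition one paragraph above, under which the first decrease during the study is the event. Follow-up lasts 36 weeks (12 + 24), so an early responder has a long time in which to leave. Each such subject would change from an early event to a long event-free record. Faster responders spend more of the study in the responded state, so at equal exit rates the arm with faster response loses the larger share of its events. The bias is therefore towards no effect.

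The second interim uses the same rule for two of the three endpoints, and under SAP 8.2 that interim feeds the decision on Cohort 3.

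**Working it through.** The plan gives no event count, hazard ratio, power or dropout rate for these endpoints, so there is no design figure to reproduce. The stated sizes agree: 3 × (8 + 4) = 36.

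**1. One subject under both sentences.** Suppose the first 1-log fall is on Day 14 and the subject leaves at the Day 140 visit. Day 1 is the first dose.
- Event definition: (13 + 1)/7 = 2.0 weeks, event.
- Censoring sentence: (139 + 1)/7 = 20.0 weeks, censored.
- Tabulation: the subject belongs to both the 'decrease' row and the 'censored' row.

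SAP 7.1.5 (missing data), SAP 9 (changes from protocol) and the protocol do not settle which sentence governs. The programming specifications are a separate document (SAP 10) and are not available here.

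**2. An invented arm of 8.** Responses at weeks 2, 3, 4, 6, 8, 12 and 16, and one non-responder. The earliest responders leave at week 20.

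| Responders leaving | Events, response stands | KM median | Events, literal rule | KM median |
|---|---|---|---|---|
| 0 | 7 | 6 weeks | 7 | 6 weeks |
| 1 | 7 | 6 weeks | 6 | 8 weeks |
| 2 | 7 | 6 weeks | 5 | 12 weeks |
| 3 | 7 | 6 weeks | 4 | 16 weeks |

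One erased responder is 1/8 = 12.5 percentage points of an active arm.

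**3. Expected number of erased events.** Assumptions, none from the documents: constant response hazard λ of 0.10 per week active and 0.03 placebo; a proportion p of subjects leaves the study, evenly over 36 weeks. The chance that a leaver has already responded is

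1 − (1 − e^(−36λ)) / (36λ).

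- Active: 36λ = 3.6, giving 1 − 0.9727/3.6 = 0.730.
- Placebo: 36λ = 1.08, giving 1 − 0.6604/1.08 = 0.389.

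| Exit p | Lost of 24 active | Lost of 12 placebo | Lost of 36 |
|---|---|---|---|
| 0% | 0 | 0 | 0 |
| 10% | 24 × 0.10 × 0.730 = 1.75 | 12 × 0.10 × 0.389 = 0.47 | 2.2 |
| 20% | 24 × 0.20 × 0.730 = 3.50 | 12 × 0.20 × 0.389 = 0.93 | 4.4 |

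Reading responses only at the scheduled visits lowers these slightly, to 1.6–3.2 active and 0.4–0.8 placebo. Hence about 2 to 4 of 36.

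**4. Hazard ratio.** A separate large-sample simulation (20,000 per arm, protocol visit weeks, assumed median response 6 versus 12 weeks, Cox model with Efron ties):

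| Exit by week 36 | HR, response stands | HR, literal rule |
|---|---|---|
| 0% | 1.97 | 1.97 |
| 10% | 1.98 | 1.87 |
| 20% | 2.00 | 1.79 |
| 30% | 1.97 | 1.70 |

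**5. Power of one contrast.** 8 versus 12, assumed hazards 0.15 and 0.03 per week (a larger effect than in step 3), two-sided log-rank test at 0.05, 3,000 simulated data sets:
- 10% exit: about 86% if the response stands, about 75% under the literal rule.
- 20% exit: about 85%, falling to about 63%.

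**The case against.** The strongest reply is that no competent programmer would read the sentence this way. The endpoint is time to the first decrease during the study, the tabulation of responders and censored subjects implies exclusive groups, and the censoring sentence can be read as a list of reasons for having no event. The mortality rule in SAP 7.5.1.12 is written in a similar list style. This stands as evidence of intent, and it is why the point concerns wording and not a demonstrated analysis choice. It does not remove the contradiction, because no sentence supplies the missing qualifier.

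Three further limits also stand.
- Stopping study drug does not trigger the rule. Protocol 3.3.2 and 8.1 direct such subjects into the follow-up assessments, so only study exit or death counts.
- The by-visit responder proportions in SAP 7.5.1.4 to 7.5.1.6 do not use this rule and would still be reported.
- The primary objective is safety, and the study is stated not to be powered for efficacy, so no confirmatory conclusion depends on this.

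Two stronger readings are tempting. A reader might infer that the last assessment date means an assessment of any type, so that time without viral-load sampling counts as time at risk. The SAP does not say this, the paragraph concerns plasma BKV only, and plasma PCR is scheduled at every post-baseline visit including FU3/ET. The two dates would differ only after a missed draw or an unscheduled contact. A reader might also infer that events will in fact be lost. With no dropout rate and no programming specifications, the documents do not show that.

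**Conclusion.** The wording is wrong as it stands. SAP 7.5.1.1 and 7.5.1.2 classify a responder who later leaves or dies in two incompatible ways; 7.5.1.3 inherits the conflict, and 8.2.2 carries it to the second interim for the 1-log and <LLOQ endpoints.

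The consequence depends on literal programming and on at least one responder leaving the study or dying. If either is absent, no events are lost. If both are present, the bias is towards no effect. On the assumed exit rates of 10–20% the damage is moderate: roughly 2 to 4 events in the whole study, and roughly 11 points (86 − 75) to 22 points (85 − 63) of power for a strong assumed effect. The hazards and exit rates are assumptions, so these figures show scale and do not predict the result. With 8 subjects per active arm, a single reclassified responder can move a median visibly.

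The sentence should be corrected, but as a clarification to secondary, unpowered endpoints.

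**What to change.** In SAP 7.5.1.1 and 7.5.1.2, replace the censoring sentence and the dating sentence that follows it with:

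> Subjects with a qualifying decrease at any post-baseline visit have an event on the date of the first such sample, whether or not they later discontinue or die. Subjects with no qualifying decrease, including those who discontinue or die without one, are censored on the date of their last post-baseline plasma BKV result.

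Sections 7.5.1.3 and 8.2.2 then follow by reference. The programming specifications should be checked against the new text. The cost is a short text change in two sections and at most one line of code, with no statistical downside. It should be made before database lock and, if still possible, before the unblinded second interim, so that the choice between the two readings is not made with results in view.

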7.5.1.2 Time (weeks) to First Decrease of BKV Plasma Viral Load to <LLOQ

The lower limit of quantitation (LLOQ) of BKV plasma viral load is 39 copies/mL BK virus DNA detected <LLOQ will be reported as 'Detected:<39 copies/mL' in data.

Time (weeks) to first decrease of BKV plasma viral load to <LLOQ is defined as the number of days from first dose date of study drug to the first decrease of BKV plasma viral load to <LLOQ during the study plus 1, then divided by 7.

Subjects who did not have a decrease of BKV plasma viral load to <LLOQ at any post-baseline visits, discontinued from the study, or died will be considered censored. For the censored subjects, the last assessment date will be used as the date of censoring.

The number and percentage of subjects with a decrease of BKV plasma viral load to <LLOQ during the study and subjects who are censored will be tabulated. Time to first decrease of BKV plasma viral load to <LLOQ will be summarized using descriptive statistics.

The median time to first decrease of BKV plasma viral load to <LLOQ and associated 95% CI will be estimated for each treatment group using the Kaplan-Meier method. The estimate of the hazard ratio for the treatment comparison between each treatment dose group and the combined placebo group along with the 95% CI will be calculated using a Cox proportional hazard model with treatment (four levels) as a factor. The log-rank p-value for the treatment comparison will be presented as well.

Time (weeks) to first decrease of BKV plasma viral load to <LLOQ will also be summarized by baseline BKV genotype.

7.5.1.3 Time (weeks) to First Decrease of BKV Plasma Viral Load to <LOD

The limit of detection (LOD) of BKV plasma viral load is 26 copies/mL. BK virus DNA detected <LOD will be reported as 'Not Detected' in data.

Time (weeks) to first decrease of BKV plasma viral load to <LOD is defined as the number of days from first dose date of study drug to the first decrease of BKV plasma viral load to <LOD during the study plus 1, then divided by 7.

Time (weeks) to first decrease of BKV plasma viral load to <LOD will be analyzed in the same manner as Time (weeks) to first decrease of BKV plasma viral load to <LLOQ.

7.5.1.4 Proportion of Subjects with ≥ 1 log Decrease of BKV Plasma Viral Load by Visit

The number and percentage of subjects with ≥ 1 log decrease of BKV plasma viral load by 1 week, 2 weeks, 4 weeks, 8 weeks, 12 weeks, 16 weeks and 36 weeks will be tabulated. The last observation by the specified timepoint will be used to identify ' ≥ 1 log decrease of BKV plasma viral load'.

The proportion of subjects with ≥ 1 log decrease of BKV plasma viral load by the specified visit will be analyzed using a logistic regression model with treatment (four levels) as a factor. For the treatment comparison between each treatment dose group and combined placebo group, the estimated odds ratio, 95% CI, and p-value will be presented.

In addition, the pairwise treatment comparisons in the proportion will be made using Fisher's Exact Test. The treatment difference estimates, the exact 95% CI, and p-values from Fisher's Exact Test will be presented.

The proportion of subjects with ≥ 1 log decrease of BKV plasma viral load by the specified visit will also be summarized by baseline BKV genotype.

7.5.1.5 Proportion of Subjects with Decrease of BKV Plasma Viral Load to <LLOQ by Visit

The number and percentage of subjects with decrease of BKV plasma viral load to <LLOQ by 1 week, 2 weeks, 4 weeks, 8 weeks, 12 weeks, 16 weeks and 36 weeks will be tabulated. The last observation by the specified timepoint will be used to identify 'decrease of BKV plasma viral load to <LLOQ'.

The proportion of subjects with decrease of BKV plasma viral load to <LLOQ by the specified visit will be analyzed using a logistic regression model with treatment (four levels) as a factor. For the treatment comparison between each treatment dose group and combined placebo group, the estimated odds ratio, 95% CI, and p-value will be presented.

In addition, the pairwise treatment comparisons in the proportion will be made using Fisher's Exact Test. The treatment difference estimates, the exact 95% CI, and p-values from Fisher's Exact Test will be presented.

The proportion of subjects with decrease of BKV plasma viral load to <LLOQ by the specified visit will also be summarized by baseline BKV genotype.

7.5.1.6 Proportion of Subjects with Decrease of BKV Plasma Viral Load to <LOD by Visit

The number and percentage of subjects with decrease of BKV plasma viral load to <LOD by 1 week, 2 weeks, 4 weeks, 8 weeks, 12 weeks, 16 weeks and 36 weeks will be tabulated. The last observation by the specified timepoint will be used to identify ‘decrease of BKV plasma viral load to <LOD’.

The proportion of subjects with decrease of BKV plasma viral load to <LOD by visit will be analyzed in the same manner as the proportion of subjects with decrease of BKV plasma viral load to <LLOQ by visit.

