7.1.4 Summary of Statistics

Summary statistics will be presented by treatment group. The placebo subjects from the cohorts will be combined. For continuous variables, the number of observations (n), mean, standard deviation, median, minimum, and maximum will be provided. For categorical variables, the frequency and percentage in each category will be displayed.

For summary statistics, the mean and median will be displayed to one decimal place greater than the original value and the measure of variability (e.g. standard deviation) will be displayed to two decimal places greater than the original value.

All efficacy analyses will be conducted using two-sided tests at the alpha=0.05 level of significance, with no adjustment for multiplicity.

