7.3.3 Demographic and Baseline Characteristics

The following demographic and baseline characteristics will be summarized:

- Age (years) and age categories (<65 years vs. ≥ 65 years);
- Sex;
- Race;
- Ethnicity
- Height (cm);
- Weight (kg);
- Body mass index (BMI) (kg/m^2) ;
- eGFR based on the CK-EPI equation ($\text{mL}/\text{min}/1.73\text{m}^2$) and eGFR categories (<15, 15-<30, 30-<60, 60-<90, and ≥ 90);
- Living donor (Yes vs. No);
- Pre-existing BKV nephropathy (Yes);

Note: Pre-existing BKV nephropathy can be identified based on the following CRF data:

- Medical history using the preferred term ‘Polyomavirus-associated nephropathy’; and
- Clinical outcome assessments indicating subjects developed or possibly developed BKV associated nephropathy at Baseline visit.

- Time from kidney transplant (days);

Time from kidney transplant (days) is calculated as the first dose date of study drug - date of kidney transplant;

- Baseline plasma viral load (copies/mL);
- Duration of BK viremia

Duration of BK viremia (days) is calculated as the first dose date of study drug - date of first reported BK plasma positive PCR

Note: the first reported BK plasma positive PCR is based on CRF data of Historical BKV Blood Sample Results and the quantitative result in copies/mL $\geq 10^3$.

- BKV genotype

Demographic and Baseline characteristics will be summarized with descriptive statistics or counts and percentages of subjects as appropriate for the ITT, MITT, and Safety Populations. Other parameters of Kidney donor profile index (KDPI) will be listed.

7.3.4 *Medical History*

Medical history will be coded to system organ class and preferred term using the Medical Dictionary for Regulatory Activities (MedDRA, Version 22.1). Counts and percentages of subjects with medical history by system organ class and preferred term will be summarized by treatment based on the ITT, MITT and Safety Populations.

All medical history will be listed by treatment and subject.

7.3.5 *Concomitant Medications*

Prior and Concomitant medications will be coded to anatomical therapeutic chemical (ATC) class and preferred term using the World Health Organization (WHO) Drug Dictionary (September 2019G B3).

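### The Cox models for time to below LLOQ and below LOD should carry baseline viral load, and the SAP should say that Fisher's exact test governs the proportion endpoints, where the logistic odds ratio may not exist

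*SAP*

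**What the plan says.** **Time to event.** SAP 7.5.1.2 (time to below LLOQ) takes the hazard ratio and its interval from a "Cox proportional hazard model with treatment (four levels) as a factor" and adds a log-rank p-value. 7.5.1.3 applies the same analysis to time to below LOD. Neither the model nor the log-rank test uses baseline viral load, which appears only as a descriptive item in 7.3.3 ("Baseline plasma viral load (copies/mL"). Neither Protocol 4.2 nor SAP 2.2.2 names a stratification factor.

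**Proportions.** From SAP 7.5.1.4 on, each viral responder proportion "will be analyzed using a logistic regression model with treatment (four levels) as a factor", reported as odds ratio, 95% CI and p-value. BKV nephropathy, graft failure and acute rejection (7.5.1.9 to 7.5.1.11) are handled the same way. The type of test behind the logistic p-value is not named, and there is no rule for an empty cell or non-convergence. The next paragraph continues "In addition, the pairwise treatment comparisons in the proportion will be made using" Fisher's exact test, with the treatment difference and an exact 95% CI.

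**Setting.** SAP section 3 plans "24 MAU868 and 12 placebo; 8 MAU868 and 4 placebo per cohort". 7.1.4 adds: "The placebo subjects from the cohorts will be combined". A final contrast is therefore 8 against 12. 7.1.4 also states: "All efficacy analyses will be conducted using two-sided tests at the alpha=0.05 level of significance, with no adjustment for multiplicity". Section 8.2.2 uses the same methods for the second interim analysis, and section 3 declares: "This study is not powered to an efficacy endpoint".

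**The concern.** There are two separate weaknesses.

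1. How far a subject's viral load must fall to get below the LLOQ or LOD is fixed by where it started. Baseline load is therefore plausibly a strong predictor of time to clearance. It is measured on everyone, yet it is used neither in the randomisation as described nor in the analysis. In groups of 8 and 12, chance imbalance is a real prospect and some precision is given away.

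2. If every subject in a group responds, or none does, ordinary maximum-likelihood logistic regression has no finite odds ratio. The analysis listed first then yields an unusable estimate and interval, and possibly a p-value near 1, beside a Fisher p-value that may be below 0.05. With no stated precedence, the choice between them would be made after unblinding.

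**Working it through.** The plan gives no power, event rate or effect size, so there is no power figure to reproduce. Its sample size is consistent: 3 × (8 + 4) = 36 = 24 + 12. Rates, decline speeds, SDs and prognostic slopes below are assumptions.

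**Distance to the threshold.** Inputs: lower bound 10^3 (SAP 7.2.2, MITT), upper bound below 10^7 (Protocol 3.2.2, exclusion 2), LLOQ 39 copies/mL (SAP 7.5.1.2).
- log10(1,000/39) = 1.41
- log10(10,000,000/39) = 5.41

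**Chance imbalance.** The SE of the difference in mean log10 load is SD × √(1/8 + 1/12) = SD × 0.456.
- SD 0.87: SE 0.397; 0.5/0.397 = 1.26; two-sided probability of an imbalance of 0.5 log or more is about 21%.
- Load uniform from 3 to 7 log10: SD = 4/√12 = 1.15; SE 0.527; 0.5/0.527 = 0.95; about 34%.

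**Cox power from assumed prognostic slopes.** True hazard ratio 4, groups 12/8/8/8, scheduled visits, Efron ties, 700 runs per cell (Monte Carlo SE up to 1.9 points); one active group against placebo.

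| Log-hazard slope per log10 | Load uniform 3–7: without / with baseline | Load normal (4.5, SD 0.9): without / with |
|---|---|---|
| 0 | 80% / 79% | 81% / 81% |
| 0.5 | 66% / 79% | 70% / 79% |
| 1.0 | 42% / 76% | 52% / 78% |

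The gain runs from about 0 (80 to 79) to 34 points (42 to 76). Null rejection was 5% to 7% with or without the covariate.

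**Cox power from assumed decline rates.** 0.10 against 0.20 log/week, 8 against 12, time to below LLOQ.
- One run of 500 trials: 63% without, 75% with baseline (12 points); null rejection 4.2% and 5.2%.
- A second set (baseline mean 4.5, SD 0.87, assay noise 0.25 log, 400 runs, Monte Carlo SE up to 2.5 points, some fits not converging), by between-subject SD of the decline rate: 0.02, 91% to 96%; 0.05, 82% to 89%; 0.10, 43% to 49%; 0.15, 25% to 29%.

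Allowing for rounding, these gains span about 3 to 12 points. For time to a 1-log fall, the second set gave 89% to 89%, 90% to 88%, 48% to 45% and 24% to 27%, which is no consistent gain.

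**How often a group sits at 0% or 100%.** For one contrast at a common low rate p, the chance is 1 − [1 − (1 − p)^8] × [1 − (1 − p)^12], ignoring the negligible chance of 100%.
- p = 5%: 1 − (1 − 0.663)(1 − 0.540) = 85%
- p = 10%: 1 − (1 − 0.430)(1 − 0.282) = 59%
- True rates 90% against 30%: 1 − (1 − 0.9^8)(1 − 0.7^12) = 1 − 0.570 × 0.986 = 44%
- True rates 50% against 10%: 29%

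**What the tests then report.**
- 8/8 against 5/12: Fisher p = (792 + 336 + 8)/77,520 = 0.0147. Stopped after 15 Newton steps, the logistic fit has coefficient 16.5, SE 708, Wald p = 0.98.
- 4/8 against 0/12: Fisher p = 70/4,845 = 0.0144. Coefficient 16.2, SE 578, Wald p = 0.98.

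The Wald figures depend on where iteration stops; the failure does not. Exact power over all 9 × 13 tables, counting a separated table as non-significant for Wald:

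| True rates | Wald | Fisher |
|---|---|---|
| 90% v 30% | 35% | 73% |
| 80% v 30% | 41% | 49% |
| 75% v 30% | 39% | 39% |
| 60% v 20% | 37% | 32% |
| 50% v 10% | 23% | 42% |

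With placebo at 30%, Wald power falls from 41% to 35% as the active rate rises from 80% to 90%.

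**The case against.** **Fisher's test is already planned.** A reader might infer that separation leaves the proportion endpoints without a valid test. The documents do not support that: Fisher's exact test and an exact CI follow directly in each proportion section and carry into 8.2.2. What stands is narrower, namely an unusable odds ratio listed first and no rule on precedence.

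**The Wald test is an inference.** The SAP names no test, and its programming specifications are a separate document. A likelihood-ratio test does not collapse: for 8/8 against 4/12 it gives p = 0.0006, with Fisher 0.0047. This stands as a limit on the p-value claim. The infinite odds ratio remains whichever test is used.

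**Baseline load is not needed everywhere.** A reader might extend the covariate to every model. A 1-log fall is already measured from baseline, and the simulations show no consistent gain there. In the logistic models, across the assumed scenarios, adding it changed power by about −3 to +7 points with Wald and −5 to +17 with Firth, and it does not remove separation. For rare clinical events it makes sparse data sparser. This objection is accepted.

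**Unadjusted tests remain valid and efficacy is secondary.** That is true. Adjustment here is about efficiency and protection against chance imbalance, not about correcting a biased test. How prognostic baseline load is cannot be read from the documents.

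**Stratification.** The documents refer randomisation details to an IWRS manual, so one can say only that no factor is stated.

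**Conclusion.** The point holds in two limited parts.

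1. For time to below LLOQ and below LOD, omitting baseline log10 viral load gives up between roughly nothing and 34 points of power under the assumed slopes, and about 3 to 12 points under assumed decline rates. If baseline load proves not to be prognostic, including it costs about one point at most. The adjusted hazard ratio is conditional on baseline load and should be labelled so.

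2. For the proportion endpoints, a group at 0% or 100% is likely at 8 against 12 (29% to 85% per contrast in the scenarios above). The logistic odds ratio and its interval are then unusable, and a Wald p-value would be near 1. Valid inference is already in the plan but is not named as governing.

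It would go too far to say that the trial's power claim fails, since none is made. The point also does not extend to deaths: 7.5.1.12 uses Kaplan–Meier and Cox, so there is no logistic or Fisher analysis to replace. The weight is that of a change that should be made before database lock, not of a flaw that invalidates the analysis.

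**What to change.** - **7.5.1.2 and 7.5.1.3:** add baseline log10 plasma viral load to the Cox model and take the treatment p-value from that model. Keep the unadjusted log-rank test as supportive; otherwise one pair of competing p-values replaces another.
- **7.5.1.4 to 7.5.1.6 and 7.5.1.9 to 7.5.1.11:** state that Fisher's exact test and the exact CI for the difference govern.
- **Odds ratios:** report them from Firth-penalised logistic regression with profile-likelihood CIs, as estimates that do not override Fisher.
- **Graft failure and acute rejection:** give counts and Fisher's test only.
- **Section 8.2.2:** apply the same rules to the endpoints it shares.
- **Not required:** the covariate for the 1-log endpoints or for rare clinical events.

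The cost is SAP wording, a Firth option in the code and one degree of freedom in two Cox models; no new data are needed. One trade-off is that Fisher's test is conservative. In one simulated setting (conditional odds ratio 12.2, baseline not prognostic) its power was 58%, against 74% for the unadjusted Firth likelihood-ratio test. Fisher is still the simpler choice because it is already pre-specified.
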